#### 6.4 Primary and Secondary Endpoints/Outcome Measures

1. To determine if an acute bout of passive, warm water therapy reduces plasma [glucose].

Secondary outcomes are to determine:

1. whether plasma [glucose] reduces more if the passive, warm water therapy is conducted before or after the OGTT?
2. whether plasma [insulin] reduces more if the passive, warm water therapy is conducted before or after the OGTT?
3. whether insulin sensitivity increases following an acute bout of warm water therapy?
4. whether fuel utilisation alters during and following an acute bout of warm water therapy?
5. whether HRV increases during or after an acute bout of warm water therapy?
6. whether eHSP increases during an acute bout of warm water therapy?
7. whether inflammatory status reduces during or after an acute bout of warm water therapy?

## 7. STUDY PARTICIPANTS

### 7.1 Study Setting

Consent, screening and familiarisation will commence at the diabetes centre and Queen Alexandra hospital. All experimental visits will take place in the Extreme Environments Laboratory at the University of Portsmouth has a 30-year history of conducting innovative human research trials. The laboratory contains world leading facilities for conducting environmental research including three bespoke environmental chambers, with temperature, humidity, simulated solar, wind and hypoxia control, and a research group involving over 20 academics and researchers.

### 7.2 Overall Description of Study Participants

Adults with a clinical diagnosis of T2DM, as defined by the WHO. A standard medical history and clinical examination will be undertaken by a research nurse or a member of the research team. Information taken during the examination will be height, weight, full blood count (analysed from a blood sample that will be collected), HbA1c, neuropathy severity and a resting ECG. ECG will be examined for irregularities and a clinical decision will be made on further participation to the study by a consultant at QA hospital.

### 7.3 Eligibility Criteria

#### Inclusion Criteria

The participants must meet ALL of the following criteria to be considered eligible for the study:

- Male or female (either post-menopausal or in the early-follicular phase (3-5 days after the onset of menstruation) of the menstrual cycle), aged 35 years or above.
- Diagnosed with T2DM as defined by the WHO.
- Participant is willing and able to give informed consent for participation in the study.
- Participant is able to understand and fully cooperate with the study protocol.

#### Exclusion Criteria

The participant may not enter / be withdrawn from the study if ANY of the following apply:

- Severe peripheral neuropathy (to the point to which they cannot sense temperature)
- Uncontrolled hypertension ( $\geq 180$  systolic / 100 diastolic mmHg)
- Taking any medication which may interfere with data interpretation or safety
- Who have had a myocardial infarction or cerebro-vascular event
- Any cardiac abnormalities which restrict hard exercise
- Current smokers or who have stopped within 3 months
- Participant is unable to understand and/or fully cooperate with the study protocol

- Any other serious medical condition which would interfere with data interpretation or safety will be excluded from participation.
- Any skin conditions including ulcerations

## 8. SAMPLING

Plasma glucose AUC is our primary outcome. No study to date has assessed the effect of hot water immersion on glucose tolerance in individuals with T2DM. Therefore, no data were available to power our primary outcome. For 90% power with an  $\alpha$ -level set at  $P < 0.05$  (two tailed), to detect a 1 SD difference, 13 volunteers are required to compare within group for placebo and active conditions. In order to counterbalance our design, 18 participants will be required to complete the testing. Therefore, we aimed to recruit 20 individuals with T2DM to account for a 10% drop-out rate typically seen in our clinical trials. Resultant effect sizes will be used to power future trials.

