### 6.3 Summary of Study Design

#### Recruitment

Participants will be recruited from adult diabetes outpatient clinics at the Queen Alexandra Hospital (Portsmouth), via a database of known individuals with T2DM from the Wessex, Diabetes, National Institute for Health Research (NIHR) Clinical Research Network and via posters and word of mouth at the University of Portsmouth. Only males and post-menopausal women will qualify for the study. Finally, the local Desmond diabetes awareness group meetings will be used to identify potential volunteers. Potential participants will either be approached by their T2DM consultant, the principal investigator, member of the research team or a research nurse. Following the participants declaration of interest, via telephone, mail, email or in clinic, they will be given a participant information sheet. A member of the research team will subsequently approach the participant  $\geq 48$  h later, to answer any questions and organise consent, screening and familiarisation (visit 1).

The design will be a balanced, randomised, within-subject comparison of three conditions (condition 1: OGTT in 23 °C air, condition 2: OGTT 30 min before 60 min in  $\sim 39^{\circ}\text{C}$  water ( $\sim 90\%$  RH), condition 3: OGTT 30 min after 60 min in  $\sim 39^{\circ}\text{C}$  water ( $\sim 90\%$  RH)). There will be 4 visits in total, visit 1 is for consent, screening and familiarisation and visits 2, 3 and 4 are experimental conditions.

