### 9.3 Randomisation

An online computer programme will be used to randomly allocate and counterbalance participants to being in one of three conditions. This will be performed by a blinded member of the research team.

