### **13.2 Analysis of Endpoints**

All data will be tested for normality. Normally distributed data will be presented as means  $\pm$  SD. Statistical analyses will be performed on SPSS software version 24.0 (Chicago, IL). For normally distributed data a one-way analysis of variance (ANOVA) will be used to identify differences between conditions for plasma [glucose] (AUC and peak), plasma [insulin], insulin sensitivity, [eHSP70], [IL-6], [IL-10], HRV, NIRS and RMR. Where significance differences are observed, post hoc test will then be performed. Where data is not normally distributed, appropriate non parametric tests will be utilised.

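### Eighteen completers out of 20 recruits do not by themselves give a counterbalanced design, and the planned ANOVA has no visit term to take up visit-to-visit drift

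*Combined protocol and SAP*

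**What the plan says.** Section 8 (Sampling) builds the sample size in three steps.

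- Power: "For 90% power with an" alpha of 0.05, "two tailed), to detect a 1 SD difference, 13 volunteers are required to compare within group for placebo and active conditions".
- Balance: "In order to counterbalance our design, 18 participants will be required to complete the testing".
- Drop-out: "we aimed to recruit 20 individuals with T2DM to account for a 10% drop-out rate typically seen in our clinical trials".

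Section 6.3 describes the design: "The design will be a balanced, randomised, within-subject comparison of three conditions". Section 9.3 (Randomisation) says "An online computer programme will be used to randomly allocate and counterbalance participants to being in one of three conditions". Neither section gives the number of orders, the block structure, or what happens to an order when a participant leaves. Section 9.5 lists reasons for withdrawal and does not mention replacement. Section 13.1 analyses only those who complete all four visits. Section 13.2 names a one-way ANOVA "used to identify differences between conditions" and mentions no visit, period or sequence term.

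**The concern.** Balance is the only reason given for going from 13 to 18 completers. Recruiting 20 secures a likely total but not equal numbers in each order, because 20 divides by neither six nor three. Which participants are lost decides whether the remaining set is balanced.

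This matters because the named analysis does not adjust for visit. The three experimental sessions are spread over about three weeks (section 10.4). If glucose response shifts from the first session to the third, an unbalanced set of completers carries part of that shift into the comparison of conditions. A balanced set removes the shift from the contrasts but leaves it in the error term unless visit is fitted. Sections 8 and 19 say that the effect sizes and confidence intervals will be used to power later work, so bias or lost precision would carry forward.

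**Working it through.** **1. The plan's own figures.** Inputs from section 8: 90% power, two-sided alpha 0.05, effect 1 SD. With 1 SD taken as one SD of the within-person difference, a paired t-test (noncentral t) has power 88.3% at n = 12 and 91.1% at n = 13, so 13 reproduces. The smallest multiple of six that is at least 13 is 18; with three orders it would be 15. So 18 points to all six orders, three people each. Drop-out: 18 / 0.90 = 20. All three figures are right.

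**2. Chance of exact balance.** Assumptions: all 20 are randomised as evenly as possible, and exactly two are lost at random.

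- Six orders (4,4,3,3,3,3): balance requires losing one person from each group of four. 4 × 4 / C(20,2) = 16/190 = 8.4%.
- Three orders (7,7,6): balance requires losing one person from each group of seven. 7 × 7 / 190 = 49/190 = 25.8%.

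**3. Bias when visit is not fitted.** I enumerated every way of placing the two extra people among six orders and every pair of losses (15 × 190 = 2,850 cases). In each I took the difference in mean visit position between conditions. Under a linear drift, that difference times the drift per visit is the bias.

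| Contrast | 95th percentile | Maximum |
|---|---|---|
| One given contrast | 0.28 visit | 0.39 visit |
| Worst of the three | 0.33 visit | 0.39 visit |

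At an assumed drift of 0.3 SD of the paired difference per visit, the bias in a given contrast is at most 0.28 × 0.3 = 0.08 SD in 95% of cases. The maximum is 0.39 × 0.3 = 0.12 SD.

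**4. Error variance at perfect balance.** Assume the ANOVA removes participant differences. With the SD of a paired difference set to 1, the within-participant residual variance is 0.5. A linear drift of d per visit adds n × 2d² to the residual sum of squares on 2(n − 1) degrees of freedom, that is d² × n/(n − 1). With n = 18 the variance ratio is (0.5 + d² × 18/17) / 0.5. The documents give no drift size, so d is a range.

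| Assumed drift d (SD per visit) | Error variance inflation |
|---|---|
| 0 | 0% |
| 0.1 | 2% |
| 0.2 | 8% |
| 0.3 | 19% |
| 0.5 | 53% |

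At d = 0.3, 18 / 1.19 = 15.1, which is like losing about 3 of the 18. The confidence interval is about 9% wider (√1.19 = 1.09).

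**5. Power for 1 SD at n = 18, exact balance.** Without drift it is about 98%. With the error variance inflated for d = 0.3 it is about 96%. Simulation without a visit term gives about 95% at d = 0.5 and about 74% at d = 1; with a visit term it stays near 98%. In the simulated cases, omitting visit did not inflate the type I error. At exact balance the test became conservative (rejection rate 1.4% at d = 0.5).

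**The case against.** The text is silent on replacing drop-outs; it does not rule replacement out. A reader might infer that vacated orders will be left empty and that balance will fail. The documents do not say so. Holding two recruits in reserve would be compatible with sections 8 and 9.3, and some of the 10% may be lost at screening before any order is used. This objection stands: the gap is one of specification, and 8.4% describes one reading of the plan.

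A reader might also infer that the trial is underpowered or that its test is invalid. Neither follows. Power for 1 SD exceeds the planned 90% at drift up to 0.3 SD, and 15 effective participants still exceed the 13 required. Randomised order makes the bias zero on average, so only chance imbalance remains.

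The documents give no evidence of drift and try to limit it: a familiarisation visit, a replicated diet, a 12 h fast and 48 h without exercise or hot baths. These measures make large drift less likely. They do not show that it is absent, and familiarisation as described includes no immersion or glucose test.

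Finally, section 13.2 does not say whether the ANOVA is within-participant. If it is not, between-person variance enters the error term and the relative cost of drift is smaller than shown. That is a separate question.

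**Conclusion.** The point holds as a gap in specification with a cheap remedy. The five completers added beyond 13 are justified only by balance, yet nothing written makes balance follow from reaching 18, and the named model has no term that would make balance less critical.

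The size is modest. Exact balance has probability 8.4% with six orders or 25.8% with three, assuming up-front randomisation of all 20 and two random losses. Bias is at most 0.39 of one visit's linear drift. Variance inflation runs from nothing to 53% over assumed drifts of 0 to 0.5 SD per visit. If there is no drift, there is neither bias nor loss. What is at stake is precision and protection against chance bias; the planned power does not need rescuing.

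**What to change.** **Main change, section 13.2.** Analyse glucose AUC with condition and visit (1, 2, 3, as categories) as fixed effects and participant as a blocking or random effect. This removes visit drift of any shape from both the contrasts and the error term, whether or not the orders are equal. Cost: 2 degrees of freedom (residual 34 to 32 with 18 completers) and a sentence of text.

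**Optional supporting change, sections 8 and 9.3.** State the number of orders and how drop-outs are handled. For example, randomise the first 18 as three per order and use the two spare recruits to fill vacated orders, allocated by the blinded team member. The total stays at 20. At independent 10% drop-out, at least 18 of 20 complete with probability 67.7%, so this gives a balanced 18 about two times in three, not always. Its other drawback is that the allocator knows the order given to a replacement. Once visit is fitted, modest imbalance no longer biases the contrasts, so this change is secondary.

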## 9. STUDY PROCEDURES

### 9.1 Recruitment

Participants will be recruited from adult diabetes outpatient clinics at the Queen Alexandra Hospital (Portsmouth), via a database of known individuals with T2DM from the Wessex, Diabetes, National Institute for Health Research (NIHR) Clinical Research Network and via posters and word of mouth at the University of Portsmouth. Additionally, participants will be recruited through primary care and via posters. Finally, the local Desmond diabetes awareness group meetings will be used to identify potential volunteers. Potential participants will either be approached by their T2DM consultant, the principal investigator, member of the research team or a research nurse. Following the participants declaration of interest, via telephone, mail, email or in clinic, they will be given a participant information sheet. A member of the research team will subsequently approach the participant  $\geq 48$  h later, to answer any questions and organise consent, screening and familiarisation (visit 1). A maximum payment of £10 will be available per visit upon request.

### 9.2 Screening and Enrolment

Consent and screening will occur at the diabetes centre at Queen Alexandra hospital. A standard medical history and clinical examination will be undertaken by a research nurse or a member of the research team at the screening visit (visit 1) after consent has been taken, including height (stadiometer, Seca, Germany), weight (Ohaus, USA), ECG and blood sample collection for lipids and biochemical markers, urea and electrolytes, HbA1c and liver function tests.

Blood pressure: Semi recumbent resting blood pressure: measurements will be performed on the morning of the screening visit; serial measurements on each participant will be made at the same time of day and same arm for each visit. The recordings will be made in quiet, comfortable, ambient laboratory conditions. Measurements will be made with a semi-automated device conforming strictly to European Hypertension Society (as adopted by

the British Hypertension Society) and American Heart Association guidelines. Five measurements will be made and the final three will be used to determine an average blood pressure.

### 9.3 Randomisation

An online computer programme will be used to randomly allocate and counterbalance participants to being in one of three conditions. This will be performed by a blinded member of the research team.

### 9.4 Study Assessments

#### *Pre-trial instructions*

Participants will be instructed to keep their normal diet and to keep it the same 48 h before each trial (they will record their intake in a diary). Additionally, they will have to fast for 12 h before the start of each visit. Participants will be instructed to consume 17 mL.kg of water and other fluids ad libitum throughout the active day (~16 h) the day before each visit [Benelam and Wyness, 2010] and 300 mL upon waking the morning of the visit. Participants will also be told to bring a bathing suit and a t-shirt to wear for the experimental visits. Additionally, participants will also be told that they cannot perform exercise or have a hot bath / sauna 48 h before each visit (can have brief (< 5 min) luke-warm showers). Visits to the laboratory should be made either via car or public transport and should not be made via physical activity e.g. cycling. Parking will be provided. At the start of each visit, plasma osmolality will be assessed via freezing point depression (model 3320 osmometer, advance instruments, USA). In line with OGTT guidelines, participants will be asked to not take their diabetes drugs on the morning of the test (hypoglycaemic agents before the fasting period are to be taken as normal). Prior to leaving the laboratory, participants will be provided with lunch, then asked to take their tablets and blood sugars checked prior to leaving.

#### *Passive heating and Core Temp*

The passive heating conditions (conditions 2 and 3) will be conducted in a thermoneutral room (~ 23°C air, ~ 90% RH), at the same time of day, with the heating taking place for 60 min in a heated pool (starting at 39°C water). Pre and post body mass will also be recorded, along with any fluid or solids going into or out of the body. Participants will firstly be cannulated lying horizontal, then will lie semi-recumbent and baseline measures taken. Depending on which condition (either 2 or 3) the OGTT or the passive heating will start first. Passive heating will start with the participant entering the pool and lying semi-recumbent on a submerged bed with their head, neck and cannulated arm above the water. Participants' rectal temperature ( $T_{rec}$ ) will be monitored so that once it reaches ~38°C the water will be cooled to ~ 38 - 38.5°C so that it will maintain  $T_{rec}$  at ~ 38.5°C ( $T_{rec}$  is still expected to rise slightly after reduction in water temperature, see below for more details). If  $T_{rec}$  reaches 39°C or above at any point, the participant will immediately be withdrawn from the study and a cooling protocol administered (see SOP attached). Additionally, if systolic BP raises above 180 mmHg or HR above 140

bpm, participants will be immediately withdrawn from the study. Passive heating will cease by winching the participant, still lying semi-recumbent, out of the immersion tank and onto a semi-recumbent bed. The participant will then be towel dried and given a blanket (to ensure maximum heat retention) and remain semi-recumbent until completion of the visit. The remainder of the visit will be conducted in the thermoneutral room.

$T_{rec}$  will be measured continuously throughout each visit using disposable rectal thermistors (Rectal temperature probe, Philips, Netherlands). Participants will self-insert the thermistor to 15 cm (this will be marked with sterilised tape) into the rectum using standard operating procedures.  $T_{rec}$  will be closely monitored throughout the passive heating conditions to ensure that it does not exceed 39°C.

### *OGTT and Insulin Sensitivity*

Insulin sensitivity will be calculated using values from both plasma glucose and plasma insulin. Multiple calculations for insulin sensitivity exist, each with their own strengths and weaknesses. Calculations used can be split into two categories: fasting indices and OGTT indices. A meta-analysis [Otten et al., 2014] of all the current surrogate measures of insulin sensitivity showed that the most valid fasting calculation to use compared with the gold standard HEC method, was the quantitative insulin sensitivity check index (QUICKI). Out of the OGTT surrogate insulin sensitivity measures Otten et al. (2014) highlighted 4 indices that were the most suitable surrogate for HEC: Stumvoll, OGIS, Matsuda and Gutt.

Following an overnight fast, blood samples will be taken for the measurement of fasting glucose and insulin levels, and this data will be used to calculate  $\beta$ -cell function via the QUICKI model [Katz et al., 2000],  $1/[\text{Log}(I_0)+\text{Log}(G_0)]$  ( $I$ =insulin,  $G$ =glucose,  $_0$ =baseline) which has been shown to have a strong positive correlation with the HEC [Otten et al., 2014]. Post-prandial glycaemic control will be measured by a 180 min OGTT (maximum of 75 g anhydrous glucose), with blood samples taken from a cannula at 0, 30, 60, 90, 120, 150 and 180 min of the OGTT, with  $\beta$ -cell function being calculated using the Stumvoll method (Equation 1).

$$0.226-0.0032 \times \text{BMI}-0.0000645 \times I_{120}-0.00375 \times G_{90}$$

**Equation 1.** Stumvoll's insulin sensitivity index equation [Stumvoll et al., 2000]

### *Thermal sensation / comfort*

Both thermal comfort and sensation will be measured using a 20 cm scale (0 = very cold/uncomfortable; 10 = neutral; 20 = very hot/comfortable; modified from Zhang et al., (2004) and recorded prior to immersion, during immersion and following the 60 min immersion, at 15 mins intervals.

### *Resting Metabolic Rate (metabolite utilization)*

Breath-by-breath changes in pulmonary gas exchange and ventilation will be non-invasively measured at rest to enable the estimation of resting metabolic rate (RMR). The assessment of pulmonary gas exchange (e.g.  $V_{O_2}$  and  $V_{CO_2}$ ) will give us the respiratory exchange ratio (RER). RER is a reliable and valid measure of fuel utilisation. To assess RMR, participants will be asked to lie down and rest for 15 mins, following this, pulmonary gas exchange will be measured via a gas analysis system for 5 min, this will be repeated every 30 min until the end of the visit. Participants will be required to use a mouth piece with a nose clip. In order to assess inspired and expired gas (volume and concentration), gases will be sampled through a capillary line attached to the face mask. A sub analysis of this breath by breath data will give us the respiratory exchange ratio (a value of 0.7 indicates only fatty acid metabolism and values of  $> 1$  indicates only glucose metabolism, any value in the middle equates to a combination of both). This is an accurate assessment of rate of energy expenditure and fuel utilisation, and will be indicative of what proportion of carbohydrate and fat is being metabolised [Blond et al., 2011]. In order to calculate the rate of carbohydrate and fat metabolism the Frayn (1983) equations will be used. Pulmonary gas analysis will be performed on all testing visits. Calibration will follow the guidelines given in the user manual produced by COSMED Omnia. Briefly, this involves calibrating the gas analyser by passing through a sample of gas with a known concentration (Oxygen: 16%, Carbon dioxide: 5%, Nitrogen: Bal) and calibrating the volume on the gas flowmeter by using a 3 L syringe to pass a known volume of air through the flowmeter.

